# • Neurologic events:

- o requiring additional exams/procedures or consultation AND selected using SMQ "demyelination" (broad and narrow), "peripheral neuropathy" (broad and narrow), and "Guillain Barre syndrome" (broad and narrow) excluding the following PTs "acute respiratory distress syndrome", "asthenia", "respiratory arrest", and "respiratory failure";
- o an additional analysis will be performed analyzing all events meeting the above SMQ criteria for neurologic events whether or not the criteria for an AESI are met (whether or not requiring additional exams/procedures or consultation).
- Any neurocognitive events:

26-Apr-2017

- o selected using the company CMQ based on HLGTs "Deliria (incl confusion)", "Cognitive and attention disorders and disturbances", "Dementia and amnestic conditions", "Disturbances in thinking and perception", "Mental impairment disorders";
- o in a second approach, neurocognitive events will be analyzed as per the CMQ developed using the FDA grouping of events based on PTs "Amnesia", "Amnestic disorder", "Anterograde Amnesia", "Behavioural and Psychiatric Symptoms of Dementia", "Change in sustained attention", "Cognitive Disorder", "Confusional State", "Delirium", "Dementia", "Dementia Alzheimer's type", "Dementia with Lewy Bodies", "Disorientation", "Disturbance in attention", "Executive dysfunction", "Frontotemporal Dementia", "Illogical Thinking", "Impaired reasoning", "Incoherent", "Judgement impaired", "Memory Impairment", "Mental Impairment", "Mental Status Changes", "Mini Mental Status Examination Abnormal", "Presenile Dementia", "Retrograde Amnesia", "Senile Dementia", "Thinking Abnormal", "Transient Global Amnesia ", "Vascular Dementia" and the LLTs "Mental State Abnormal Aggravated", "Thinking Slowed";
- o in a third approach, neurocognitive events will be analysed using company CMQ or FDA CMQ.

Analyses of allergic drug reactions and local injection sites reactions and neurologic events will also be provided using the drop-down on the e-CRF AE page as a second approach.

All analyses described above as additional are not AESI, but AE groupings that will be explored.

In addition the following grouping of events will be provided:

- Hepatic disorder events using SMQ "Hepatic disorder";
- Diabetic complications using HLGT "Diabetes Complications", HLT "Diabetes Mellitus (incl subtypes)", and HLT "Carbohydrate tolerance analyses (incl diabetes)", PT "Hyperglycaemia", PT "Hyperglycaemic unconscioussness", PT "Hyperglycaemic seizure", excluding PT "Blood glucose decreased", and PT "Glycosylated haemoglobin decreased";
- Hypoglycemia events using CMQ "Hypoglycemia" (narrow only).

### 2.1.4.2 Deaths

The death observation periods are per the observation periods defined above:

- Death on-study: deaths occurring during the on-study observation period;
- Death on-treatment: deaths occurring during the TEAE period;
- Death post-study: deaths occurring after the last planned protocol visit.

# 2.1.4.3 Laboratory safety variables

Clinical laboratory data consists of blood analysis, including hematology, clinical chemistry, and urinalysis. Clinical laboratory values, after conversion, will be analyzed as international and conventional units.

Blood samples for clinical laboratories will be taken at Week -3, Week 0 (please refer to study protocol for requirements, some safety laboratory data are only required at Week 0 per judgment of investigator), Week 8, Week 12, and Week 24/EOT. The laboratory parameters will be classified as follows:

# Hematology

- o **Red blood cells and platelets**: complete blood cell count (CBC) including hematocrit, hemoglobin, red blood cell (RBC) count, red blood cell distribution width (RDW), and platelets;
- White blood cells: white blood cell (WBC) count with differential count, neutrophils, lymphocytes, monocytes, basophils and eosinophils.

# • Clinical chemistry

- o **Metabolism**: plasma glucose, total protein, albumin, HbA1c, creatine phosphokinase;
- o Electrolytes: sodium, potassium, chloride, bicarbonate, calcium, phosphorous;
- o **Renal function**: blood urea nitrogen, creatinine, uric acid, eGFR;
- Liver function: alanine aminotransferase (ALT), aspartate aminotransferase (AST), alkaline phosphatase (ALP), gamma-glutamyl transferase (GGT), lactate dehydrogenase (LDH) and total bilirubin (in case of total bilirubin values above the normal range, differentiation into conjugated and non-conjugated bilirubin will occur automatically);
- **Pregnancy test (at screening)**: Serum β-human chorionic gonadotropin (women of childbearing potential) status (Positive/Negative);
- **Hepatitis screen**: Hepatitis C antibody (at screening, Week 24 and in case of transaminases elevation), Hepatitis B surface antigen (screening only). If tests are repeated or confirmatory test are performed, all results will be described;
- o **Other parameters**: thyroid stimulating hormone (TSH) (for patients on thyroid hormone replacement therapy) at screening only.

Urine samples will be collected at Screening (Week -3) and Week 24/or early termination as follows:

- o **Urinalysis** quantitative analyses: pH, specific gravity, presence of blood, proteins, ketones, nitrates, leukocyte esterase, uro-bilinogen, bilirubin and glucose;
- o **Spot urine testing**: albumin, creatinine for albumin/creatinine ratio calculation;
- Standard microscopy (if abnormal dipstick): presence of red blood cells (RBC), RBC clumps, WBC, WBC clumps, epithelial cells (transitional, renal tubular, and

26-Apr-2017

squamous), casts (hyaline, epithelial, WBC, RBC, granular, fatty, cellular, broad, waxy), crystals (triple phosphate, calcium oxalate, calcium phosphate, calcium carbonate, uric acid, amorphous, ammonium biurate, bilirubin, leucine, tyrosine, cystine), bacteria, yeast-budding, yeast-hyphae, trichomonas, oval fat body, fat, mucous, and sperm;

• **Pregnancy test** (women of childbearing potential): urine pregnancy test at Week 0 and Week 24/early termination visit.

Technical formulas are described in Section 2.5.1.

# 2.1.4.4 Vital signs variables

Vital signs include: height (in cm at baseline), weight (in kg), BMI (in kg/m²), HR (in bpm), SBP and DBP in sitting position (in mmHg).

# 2.1.4.5 Electrocardiogram variables

Not applicable.

#### 2.1.5 Pharmacokinetic variables

Total and free PCSK9 concentrations in serum are assessed at baseline (Week 0), Week 12, and Week 24.

### 2.1.6 Pharmacodynamic/genomics endpoints

Not applicable.

# 2.1.7 Quality-of-life endpoints

### 2.1.8 Health economic endpoints

Not applicable.

### 2.1.9 Diabetes related endpoints

The analyses of diabetes-related endpoints will include the following parameters:

- Absolute change in HbA1c in % and mmol/mol from baseline to Weeks 12 and 24
- Absolute change in FPG in mg/dL and mmol/L from baseline to Weeks 12 and 24

Version number: Final

26-Apr-2017

- Absolute change in number of glucose lowering treatments from baseline to Weeks 12 and 24:
  - o For non-insulin treatments each unique treatment will be counted as 1, whereas for insulin treatments, insulin will be counted as 1 in total even if the patient is taking more than one insulin treatment (for example, a patient on glargine monotherapy will have "1" glucose lowering treatment, and a patient on glargine and humalog without additional glucose lowering treatments will also have "1" glucose lowering treatment).
  - o For combinations of insulin and non-insulin treatment, the insulin will be counted as 1 and each non-insulin in the combination will be counted as 1 (for example, ideglira would count as "1" for the insulin degludec and "1" for the liraglutide, i.e. a total of "2" glucose lowering treatments).

#### 2.1.10 Anti-alirocumab antibodies

Anti-alirocumab antibodies (status, neutralizing status and titer) will be collected at Week 0, Week 12, and Week 24.

# 2.1.11 Nutritional counseling

Nutritional counseling status will be collected at Week 0, Week 4, Week 8, Week 12, Week 20 and Week 24.

#### 2.2 DISPOSITION OF PATIENTS

This section describes patient disposition for both patient study status and the patient analysis populations.

Screened patients are defined as any patients who signed the informed consent.

Randomized patients consist of all screened patients who are recorded in the IVRS/IWRS database (if randomized to usual care) and with a treatment kit allocated (if randomized to alirocumab), regardless of whether the treatment kit was used or not. Patients treated without being randomized or treated with a treatment kit before the randomization will not be considered as randomized and will not be included in any analysis population. The safety experience of patients treated and not randomized will be reported separately and these patients will not be in the safety population.

For any patient randomized more than once, only the data associated with the first randomization will be used in any analysis population. The safety experience associated with any later randomization will be assessed separately.

For patient study status, the total number of patients in each of the following categories will be presented by randomization stratum (for strata with at least 10% of patients) and in the pooled data in the clinical study report using a flowchart diagram or summary table:

Property of the Sanofi Group - strictly confidential

- Version number: Final
- Screened patients;
- Screen failure patients and reasons for screen failure;
- Non-randomized but treated patients;
- Randomized patients;
- Randomized but not treated patients and reason for not treated (not applicable for patients randomized to usual care arm without intent to prescribe an additional LMT);
- Randomized and treated patients;
- Patients who completed the study treatment period as per protocol;
- Patients who discontinued the study treatment and main reason for permanent treatment discontinuation (not applicable for patients randomized to usual care arm without intent to prescribe an additional LMT);
- Patients who completed the study period as per protocol;
- Patients who discontinued the study and main reason for study discontinuation;
- Status at last study contact.

For all categories of patients (except for the screened and non-randomized categories) percentages will be calculated using the number of randomized patients as the denominator.

Reasons for treatment discontinuation will be supplied in tables giving numbers and percentages by treatment group. A listing of patients who prematurely discontinued study treatment with further reason provided in free text will be provided.

The incidence of premature treatment discontinuation (irrespective of the reason) and premature treatment discontinuation due to AEs will be presented graphically by treatment group on randomized and treated patients (as treated), using Kaplan-Meier method.

The incidence of premature study discontinuation (irrespective of the reason) and premature study discontinuation due to AEs will be presented graphically by treatment group on randomized and treated patients (as treated), using Kaplan-Meier method.

Patients with insufficient post-treatment follow-up will be described on the safety population by treatment group. Number and percentage of patients with insufficient follow-up, quantitative (in weeks) and qualitative ( $<1, \ge 1$  to  $<3, \ge 3$  to  $<5, \ge 5$  to  $<7, \ge 7$  to <9 weeks) duration of follow-up will be presented by treatment arm. A patient is considered with insufficient post-treatment follow-up in the case of his/her last post-treatment phone-call is:

- For patients receiving alirocumab: less than 9 weeks after the last open-label alirocumab injection, unless patient died before
- For patients receiving another LMT in the usual care arm:
  - o less than 9 weeks after the last dose of usual care treatment or
  - o before Week 31,

26-Apr-2017

whichever comes first, unless patient died before

- For patients randomized to usual care without LMT:
  - o less than 9 weeks after the last on site study visit or
  - before Week 31,
     whichever comes first, unless patient died before.

All major deviations potentially impacting efficacy analyses, randomization, and drug-dispensing irregularities, and other major or critical deviations will be summarized in tables giving numbers and percentages of deviations by treatment group. Patients excluded from the ITT population will be listed as well as patients with major deviation potentially impacting efficacy analyses not resulting in exclusion from ITT population. These deviations are listed in the data review and surveillance plan.

Additionally, the following analysis populations will be summarized by treatment group:

- Randomized population;
- Efficacy population: ITT population;
- Safety population;
- PCSK9 population;
- ADA population.

Definitions of the study populations are provided in Section 2.3.

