## 6 STUDY DESIGN

#### 6.1 DESCRIPTION OF THE PROTOCOL

This is a Phase 3b/4 randomized, open-label, parallel group study to assess the efficacy and safety of alirocumab administered by subcutaneous (SC) injection versus usual care in patients with Type 2 diabetes and mixed dyslipidemia at high CV risk with non-HDL-C not adequately controlled with maximally tolerated statin therapy. The study will be multinational and multicenter. The study consists of a screening period of up to 3 weeks, an open-label treatment period (OLTP) of 24 weeks, and a safety observation period of 8 weeks.

Patients, unless they are statin intolerant, will be taking a stable, maximally tolerated dose of statin therapy without other lipid modifying therapies (LMT). Statin dose and dose regimen should be stable throughout the entire study duration including for 4 weeks prior to the screening period and from screening to the end of the open label treatment period. Patients should continue to follow a cholesterol lowering diet during the study, however, the Investigator may reinforce diet recommendations according to local/regional guidelines. Patients should be receiving treatment for diabetes in accordance with local/regional standards of care. Changes to antihyperglycemics should be limited and made only in circumstances where it is clinically needed.

Randomization will be unbalanced (2:1, alirocumab:usual care).

The usual care arm includes the option to continue on the maximum dose of statin that is tolerated by the patient without the addition of a new LMT at randomization, or may initiate either ezetimibe, fenofibrate, omega-3 fatty acids, or nicotinic acid at randomization for the remainder of the 24-week treatment period. Initiation of usual care treatment (IMP) should start as soon as possible after randomization, but no later than 7 days from the day of randomization.

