## 8.1.1.2 Timing of administration

During the screening period, patients or the designated person will have to perform a placebo self-injection training using a prefilled pen, before randomization and the first alirocumab injection.

At the randomization visit, the first alirocumab injection will be done at the site by the patient or another designated person (such as spouse, relative, etc) under direct site staff supervision. Patients will be monitored at the investigational site for at least 30 minutes after this first injection in this study. If the designated person changes during the course of the study, the new designated person will need to be trained with placebo prior to administering alirocumab to the patient.

Alirocumab SC injections will then be performed outside of the clinic, Q2W up to the last injection. If the injection is scheduled to take place on the same date as the site visit, then alirocumab should be administered after the blood sampling has been completed. In exceptional cases, if a patient prefers to have the injection performed at the study site and provisions are able to be made to accommodate the administration of injections at the site, it may also be allowed.

18-Nov-2015 Version number: 1

Alirocumab should be administered SC Q2W, ideally at approximately the same time of the day; however, it is acceptable to have a window period of  $\pm 3$  days. The time of the day is based upon the patient's preference.

If by mistake or due to other circumstances an injection is delayed by:

- more than 7 days from the missed date or completely missed, then the patient should return to the original schedule of alirocumab administration without administering delayed injections.
- less than or equal to 7 days from the missed date, then the patient should administer the delayed injection and then resume the original schedule of alirocumab administration.

Please note that injections should not be administered within less than 7 calendar days. Please refer to Section 10.4.1.3 for the definition of overdose with alirocumab.

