#### 8.1.2 Usual care treatment

There are five options available in the usual care arm including the option to add no additional LMT on top of the maximum dose/regimen of statin that is tolerated by the patient or to start one of the following treatments: ezetimibe, fenofibrate, omega-3 fatty acids or nicotinic acid. All patients, regardless of the usual care option that has been selected, should continue on the maximum dose/regimen of statin (non-IMP) that is tolerated by the patient.

The following drugs are identified as IMP:

- Ezetimibe,
- Nicotinic acid,
- Fenofibrate,
- Omega-3 fatty acids

The pharmaceutical form, dose and number of units per administration and timing of dosing of usual care treatment will be determined by the Investigator, and prescribed as per the Investigator's usual practice in accordance with local standard of care.

The usual care IMP will be financially supported by Sanofi. The Investigator will provide the patient with a prescription for usual care IMP at randomization and at Week 12 to cover the treatment period. The commercially available products will be delivered to the patient by the Investigator or other authorized persons (eg, pharmacist) according to the prescription.

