  - The first alirocumab IMP administration will take place at the study site, but only after the collection of the fasting blood samples. Close supervision, feedback and further training to be provided for alirocumab administration. The patient should be observed for at least 30 minutes after the injection.
- If randomized to usual care, provide prescription based on treatment entered into IVRS, as applicable, see Section 8.1.2
- Provide the Patient diary and instruct the patient to complete it
- Reminders to be communicated to the patient
  - An appointment will be given for the next phone call and study site visit.
  - Remind patient to be in fasting conditions (ie, overnight, at least 10-12 hours fast and refrain from smoking) for next study site visit. Also, alcohol consumption within 48 hours and intense physical exercise within 24 hours preceding the next study site visit are discouraged.

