#### 1.4 STUDY PLAN

This is a Phase 3b/4 randomized, open-label, parallel group study to assess the efficacy and safety of alirocumab administered by subcutaneous injection versus usual care in patients with Type 2 diabetes and mixed dyslipidemia at high CV risk with non-HDL-C not adequately controlled with maximally tolerated statin therapy. The study will be multinational and multicenter. The study consists of a screening period of up to 3 weeks, an open-label treatment period (OLTP) of 24 weeks, and a safety observation period of 8 weeks.

Patients, unless they are statin intolerant, will be taking a stable, maximally tolerated dose of statin therapy without other LMTs. Statin dose and dose regimen should be stable throughout the entire study duration including for 4 weeks prior to the screening period and from screening to the end of the OLTP. Patients should continue to follow a cholesterol lowering diet during the study, however, the Investigator may reinforce diet recommendations according to local/regional guidelines. Patients should be receiving treatment for diabetes in accordance with local/regional standards of care. Changes to antihyperglycemics should be limited and made only in circumstances where it is clinically needed.

The usual care arm includes the option to continue on the maximum dose of statin that is tolerated by the patient without the addition of a new LMT at randomization, or may initiate either ezetimibe, fenofibrate, omega-3 fatty acids, or nicotinic acid at randomization for the remainder of the 24-week treatment period. Initiation of usual care treatment should start as soon as possible after randomization, but no later than 7 days from the day of randomization.

The Investigator will select the most appropriate LMT for the patient prior to randomization (consisting of either no additional LMT but continuing on maximum tolerated statin, ezetimibe, fenofibrate, omega-3 fatty acids or nicotinic acid) and enter this information into the IVRS. If the patient is randomized to open-label alirocumab, the Investigator will not institute the LMT option that was selected and entered into IVRS but instead treat the patient with open-label alirocumab. If the patient is randomized to usual care (non-alirocumab), the Investigator will initiate treatment with the LMT option that was selected and entered into IVRS, as applicable, in addition to continuing the patient on the maximum tolerated dose of statin.

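### The study-discontinuation curves in SAP 2.2 leave out randomized patients who go undosed, most likely usual-care patients who withdraw before their first LMT intake

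*SAP*

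**What the plan says.** SAP 2.2 plans Kaplan-Meier displays of two things: stopping study treatment and leaving the study, each for any reason and due to adverse events. Both use the same patient set. For leaving the study, the text reads "premature study discontinuation due to AEs will be presented graphically by treatment group on randomized and treated patients (as treated), using Kaplan-Meier method". It gives no time origin for these curves.

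The disposition table in the same section has a different base: for all categories after randomization, "percentages will be calculated using the number of randomized patients as the denominator". One of its rows begins: "Randomized but not treated patients and reason for not treated (not applicable for patients randomized to usual care arm without intent to prescribe an additional". So the SAP recognises randomized patients who are not treated, and exempts only usual-care patients for whom no LMT was intended.

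The first dose reaches the two arms differently:

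- **Alirocumab.** Protocol 8.1.1.2: "At the randomization visit, the first alirocumab injection will be done at the site by the patient or another designated person". Protocol 10.1.2.1 agrees: "The first alirocumab IMP administration will take place at the study site, but only after the collection of the fasting blood samples".
- **Usual care with an LMT.** Protocol 8.1.2: "The Investigator will provide the patient with a prescription for usual care IMP at randomization and at Week 12 to cover the treatment period". Protocol 6.1 says that initiation "should start as soon as possible after randomization, but no later than 7 days from the day of randomization", and SAP 1.4 repeats this.

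**The concern.** Stopping a drug presupposes having started it, so a treated set suits the treatment-discontinuation curve. Leaving the study does not presuppose a dose. It is possible from the moment of randomization, and in an open-label trial patients know their arm from that moment. Requiring a first dose is a condition met after randomization, and the chance of failing it differs by arm. In usual care there can be up to a week between allocation and first intake, during which a patient can withdraw. In the alirocumab arm the first injection belongs to the randomization visit.

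At stake is how loss after randomization is shown. This is the only planned display of time to study dropout by arm, and a reader would use it to judge whether patients left one arm sooner or more often than the other.

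**Working it through.** The plan attaches no figure to this point, so there is nothing to reproduce. The check has three parts.

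**1. Who is off the curve**

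| Randomized patient who leaves undosed | Treated as implied by the SAP 2.2 not-treated row | Treated meaning the safety population (SAP 2.3.2) |
|---|---|---|
| Usual care, LMT intended | excluded | included |
| Usual care, no additional LMT | included (row not applicable) | included |
| Alirocumab, kit allocated but unused | excluded (unlikely, given on-site dosing) | excluded |

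The SAP does not define treated for usual care. Protocol 11.3.3 equates treated patients with the safety population when it defines the antibody set, and that population takes in every patient randomized to usual care. The first reading is better supported for two reasons. The not-treated row exempts only the no-LMT option. And SAP 2.2 names the safety population for its insufficient-follow-up summary, just after the curves, but not for the curves. Neither reading covers all randomized patients.

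**2. Whether these patients are in the primary model**

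The ITT population needs at least one non-HDL-C value inside an analysis window (SAP 2.3.1.1). The earliest window opens on Day 15 (SAP 2.5.3, Table 2), and the first scheduled post-baseline lipid sample is at Week 8 (Protocol 1.2). LMT is due to start within 7 days. A patient who leaves before that therefore normally has no value in any window, and is outside both the ITT population and the MMRM.

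**3. Size on the first reading**

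Input from the documents: 140 usual-care patients (SAP 1.1). Assumptions, not in the documents: k patients leave before first LMT intake and m leave later. Using simple proportions and ignoring censoring:

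- all randomized: (k + m)/140
- treated only: m/(140 − k)

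| m | k | All randomized | Treated only | Gap (points) |
|---|---|---|---|---|
| 7 | 1 | 8/140 = 5.7% | 7/139 = 5.0% | 0.7 |
| 7 | 3 | 10/140 = 7.1% | 7/137 = 5.1% | 2.0 |
| 7 | 7 | 14/140 = 10.0% | 7/133 = 5.3% | 4.7 |
| 14 | 1 | 15/140 = 10.7% | 14/139 = 10.1% | 0.6 |
| 14 | 3 | 17/140 = 12.1% | 14/137 = 10.2% | 1.9 |
| 14 | 7 | 21/140 = 15.0% | 14/133 = 10.5% | 4.5 |

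Each such patient hides roughly 0.6 to 0.7 points.

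A plausible k can only be assumed. If 50% of usual care (range 30 to 80%) is assigned an LMT and 3% of those (1 to 8%) leave before first intake, then k = 140 × 0.5 × 0.03 = 2.1, with a range from 140 × 0.3 × 0.01 = 0.4 to 140 × 0.8 × 0.08 = 9.0.

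**The case against.** The strongest reply is that little is lost. The curves are descriptive and no test or estimate uses them. The disposition table counts study discontinuations, and untreated patients with reasons, over all randomized patients. SAP 2.2 also lists patients excluded from ITT and gives the sizes of the randomized, ITT and safety populations by treatment group. An early leaver can be traced through these. All of this stands and keeps the severity low. It is not a full answer: the disposition table is specified by stratum and pooled, without naming treatment group, and none of these outputs shows timing by arm.

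Three stronger inferences are tempting, and the documents do not support them:

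- A reader might infer that the omitted patients are the source of missing Week 24 values in the MMRM, so that the curve conceals a threat to its missing-at-random assumption. First-week leavers are normally not in that model at all. A patient who never takes the LMT but stays to Week 8 and then leaves would be in ITT and off the curve, but nothing in the documents indicates how often that would happen.
- A reader might infer that the curve makes the arms look more alike than they were. That holds only if usual-care dropout is the higher of the two. If alirocumab dropout is higher, removing usual-care leavers widens the apparent difference. The documents give no dropout rates.
- A reader might infer that table and curve contradict each other. They are two displays with two labelled bases.

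The wording objection also stands in part. Treated is undefined for usual care, and the safety-population reading reverses which arm loses patients. It does not rescue the curve, which still falls short of all randomized patients.

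**Conclusion.** The point holds as a low-severity matter of display. The study-discontinuation curves rest on a dosing condition that has no bearing on whether a patient left the study. On the better-supported reading they understate early usual-care dropout by about 0.6 to 0.7 points per affected patient out of 140, and alirocumab is almost untouched. That reading takes an LMT-assigned patient with no intake as untreated, and patients in the no-additional-LMT option as remaining in the curve. The number affected cannot be derived from the documents, nor can the effect on apparent balance between arms. The curve for discontinuation due to adverse events is probably affected less, since withdrawal over the allocation itself is not an adverse event. No efficacy conclusion depends on either curve.

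**What to change.** In SAP 2.2, draw both study-discontinuation curves (any reason, and due to adverse events) on all randomized patients, by randomized group, with time counted from randomization. Keep the randomized-and-treated set, grouped as treated, for the treatment-discontinuation curves only. A short definition of treated for usual care would settle the ambiguity where that set is retained.

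The cost is one sentence, plus the optional definition. The date and reason of premature study discontinuation are already source data (Protocol 10.2). No new data, test or alpha is involved.
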